Cover Page for ClinicTrials.gov

Document:

IN-HOME Study Protocol and Statistical Analysis Plan

Official Study Title:

Testing Preliminary Effectiveness of a Community Health Worker (CHW) Training Program to Support African American and Latino Male Caregivers of Older Adults

Document Date:

January 1, 2023

IN-HOME feasibility evaluation

I. Original proposal narrative

The Phase 1 feasibility evaluation, a RCT with a two-group pre–post design with 87 CHWs will explore the following question: To what extent is IN-HOME exposure (treatment) associated with greater CHW knowledge, skills, and perceived self-efficacy to conduct outreach to reduce caregiver burden for African American and Latino male informal caregivers of older adults compare to CHWs reviewing caregiver information from AARP’s English “Care at Home” resource page (control)? What is the relation between demographic characteristics (e.g., age and race/ethnicity) and experimental differences in knowledge, skills, and perceived self-efficacy? What is the extent of difference in outcomes between treatment and control participants?

We will enroll 60 CHWs per arm. Eligible participants will (1) be at least 18 years old, (2) self-identify as a CHW, (3) live in the United States, (4) conduct outreach, to African American and Latino male informal caregivers, (5) have at least six months of field experience and (6) be an active CHW within the last six months.

We will randomly assign participants to the treatment and control conditions. Any stratification based on potentially confounding factors will be done by using covariates in the full analyses. Treatment participants will complete a pretest before and a posttest after viewing the IN-HOME prototype. Control participants will complete a pretest before and a posttest after reviewing caregiver information from AARP’s English “Care at Home” resource page.

IN-HOME is feasible if the treatment group shows statistically significant higher mean scores in knowledge, skills, and perceived self-efficacy at posttest compared to the control group. We will use covariate-adjusted ANCOVA to control for group differences (e.g., received caregiver training before) that may confound outcomes. We will use two-tailed tests to identify potential iatrogenic effects.

II. IN-HOME study research questions

1. To what extent is IN-HOME exposure (treatment) associated with greater CHW knowledge, skills, and perceived self-efficacy to conduct outreach to reduce caregiver burden for African American and Latino male informal caregivers of older adults compare to CHWs reviewing caregiver information from an online resource (control)?
 - What is the relation between demographic characteristics (e.g., age and race/ethnicity) and experimental differences in knowledge, skills, and perceived self-efficacy?
2. What is the extent of difference in outcomes between treatment and control participants?
 - What is the relation between demographic characteristics (e.g., age and race/ethnicity) and experimental differences in knowledge, skills, and perceived self-efficacy?

3. To what extent do CHWs exposed to IN-HOME show greater gains in knowledge compared to the control group?
 - What is the relation between demographic characteristics (e.g., age and race/ethnicity) and experimental differences in knowledge, skills, and perceived self-efficacy?
4. To what extent do CHWs exposed to IN-HOME are more prepared to provide support to male caregivers compared to the control group?
 - What is the relation between demographic characteristics (e.g., age and race/ethnicity) and experimental differences in knowledge, skills, and perceived self-efficacy?

For specific hypotheses, see the research question and hypotheses document, located here:
S:\Projects\IN-HOME\Feasibility evaluation\Methods and analysis

III. IN-HOME study summary

Study design: Randomized controlled trial with a two-group online pretest/posttest design.

Study population and sites: The study population will include active CHWs. The study will be conducted online and include participants recruited by six CHW organizations in Alabama, Georgia, Florida, Virginia, Illinois, and Texas.

Treatment regimen: Treatment group participants will view the IN-HOME prototype. Control group participants will view materials from AARP's English "Care at Home" resource page.

Randomization: The research assistant will randomly assign participants to the control or treatment group after they consent to the study.

Institutional Review Board (IRB): KDHRC received approval for pilot testing materials on May 2, 2023 IRB # 00005850.

The final approved IRB package can be found at: S:\IRB\Reviews\Reviews - general\2023\2023-02-01 - 2023-0213 - In Home\12 - Amended approval packet

IV. Pre-launch survey review

KDHRC conducted a pre-launch review of the survey instrument to ensure its clarity, reliability, and validity before full-scale use. Internal staff tested the eligibility, consent, pretest, and posttest links to confirm that the surveys were ready to launch. After reviewing the survey questions and testing the survey, we submitted an amendment request to the IRB for modifications and additions. Staff retested the links.

The amendment request can be found here: S:\IRB\Reviews\Reviews - general\2023\2023-02-01 - 2023-0213 - In Home\10 - Amendment request

V. Recruitment

We contracted with six sites with CHW-related programs. All sites received a brief training video to explain IN-HOME and provide an overview of the study requirements, time commitment, and consent process. After completing the training call, sites will begin recruitment using KDHRC-developed and IRB-approved recruitment materials. Sites shared the recruitment materials with their CHWs via email, newsletter, fliers, in-office communications (e.g., Slack) and social media posts. The recruitment period began upon receiving IRB approval, and ended when we received enough participants for power for analysis.

The recruitment period for IN-HOME lasted from May 15, 2023 to August 16, 2023.

IV. Data collection

- Recruitment numbers (aimed): 123 CHWs
- Recruitment numbers (actual): 123 CHWs consented [52 control; 55 treatment]
- Dates: May 15, 2023 – August 16, 2023

V. Data cleaning

1. Make changes in Alchemer (if required)
2. Download pretest and posttest from Alchemer and save in the “raw data” folder – do not make any changes to this data.
 - Location (control group): S:\Projects\IN-HOME\Feasibility evaluation\Raw data\Control\Final control group raw data
 - Location (intervention group): S:\Projects\IN-HOME\Feasibility evaluation\Raw data\Treatment\Final treatment group raw data
 - File is password protected with standard data protection password. See [name] for password.
3. Copy the raw data file exported from Alchemer into the “Manipulated data folder”
 - Location: S:\Projects\IN-HOME\Feasibility evaluation\Manipulated data
4. Merge the posttest treatment and posttest control surveys together to form a single posttest file.
 - Archive separate posttest treatment and posttest control surveys.
 - Save combined posttest survey files as _COMBINED.
5. Merge pretest and posttest data by matching pre- and posttest responses by participant ID.

- Compare participant ID (last-initials-state) between pre and posttest responses.
- If the participant matches, merge the pre and posttest variables.
- Archive pretest and posttest survey files.
- Save merged survey files as _MERGED.

6. Delete observations, if applicable.
7. Clean data in preparation for data analysis.

VI. Data analysis

1. Create dichotomous variables for incorrect and correct answers
 - a. For the knowledge and skills variables, we will code correct answers as '1' and incorrect answers as '0'.
 - b. The new variable name will use “_correct” (e.g. q1_t1_correct).
2. Create a dummy variable for treatment.
 - a. For all participants in the treatment group, we will code the variable “treatment” with a '1' and control group participants with a '0'.
3. Create composite variables for the knowledge, skills, and self-efficacy questions.
 - a. Create composite variables for each participant that sums all their answers for each outcome and divides them by the total number of questions to create composite scores, ranging from 0 to 100 (e.g., a composite knowledge score of 100 means that a participant correctly answered all knowledge questions on the pretest).
 - b. The new variable names will be “know_comp_t1,” “know_comp_t2,” “att_comp_t1,” “att_comp_t2,” “se_comp_t1,” “se_comp_t2,” “int_comp_t1,” and “int_comp_t2.”
4. Create “gain” or “differences” score for the composite variables.
 - a. Subtract the t1 composite variables from the t2 composite variables to get the change in composite score from pretest to posttest for each outcome area.
 - b. The new variable names will be “know_comp_diff,” “att_comp_diff,” “se_comp_diff,” and “int_comp_diff.”

Methods

- Between groups t-tests on each outcome’s composite score at pretest and posttest.
- Within group t-tests between each outcome’s pretest and posttest composite scores.

- Regression analyses using each primary outcome's posttest composite score as the dependent variable and group assignment as the primary independent variable, while controlling for participant characteristics at baseline including race, ethnicity, age, sex, education, time as CHW, paid/volunteer status, having over 16hrs of training, number of usual topics outreach is conducted on, and whether participants had been trained previously in older adult care.

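### No analysis in this document estimates whether the treatment-control difference varies with age, race or ethnicity, although the demographic sub-question most naturally asks that

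*Combined protocol and SAP*

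**What the plan says.** The sub-question "What is the relation between demographic characteristics (e.g., age and race/ethnicity) and experimental differences in knowledge, skills, and perceived self-efficacy" stands once in section I (Original proposal narrative) and under each of research questions 1 to 4 in section II, five times in all.

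The analyses offered are these:

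- Section VI, Methods: t-tests between the arms at pretest and at posttest. They involve no demographic variable.
- Section VI, Methods: "Within group t-tests between each" outcome's pretest and posttest scores. These also involve no demographic variable.
- Section VI, Methods: a regression with the "posttest composite score as the dependent variable and group assignment as the primary independent variable". Demographics enter this model only as adjustment terms; it is fitted "while controlling for participant characteristics at baseline including race, ethnicity, age, sex, education" and further baseline characteristics. No product term is named.
- Section I: "We will use covariate-adjusted ANCOVA to control for group differences (e.g., received caregiver training before) that may confound outcomes".
- Section I: "Any stratification based on potentially confounding factors will be done by using covariates in the full analyses".

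Section VI also creates gain scores, but no listed analysis relates them to demographics. No interaction, moderator, subgroup or stratum-specific analysis is named anywhere. Section II adds: "For specific hypotheses, see the research question and hypotheses document, located here". That file is not part of the document.

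**The concern.** Each sub-question sits under a treatment-control comparison, so the experimental difference is most naturally the difference between arms. Relating that difference to age or race/ethnicity is effect modification, and it needs a group-by-characteristic term or effects estimated by stratum. Covariate adjustment supplies neither, because it returns one group effect that is taken to be common to everyone.

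Followed as written, the plan would report an average effect per outcome and could not say whether that effect differs by age, race or ethnicity. It would, however, produce outputs that look like an answer: demographic coefficients from the regression, and the change in the group difference after adjustment. A report could offer either one in reply to the sub-question.

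**Working it through.** **1. What each planned analysis can show about the sub-question**

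| Analysis | What it estimates | Effect modification? |
|---|---|---|
| Between-group t-test | Unadjusted group difference | No |
| Within-group t-test | Mean gain in each arm | No |
| Posttest regression / ANCOVA | One adjusted group effect, plus demographic main effects | No |
| Unadjusted versus adjusted difference | Whether demographics account for the group difference | No |

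The demographic coefficients describe posttest level, or gain if the pretest is a covariate. If posttest = a + b·group + c·demographic + d·pretest, subtracting the pretest from both sides changes only d to d − 1, so c is the same for posttest and gain. The listed covariates do not name the pretest, so which of the two would be estimated is unresolved. Neither is effect modification.

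**2. Can the planned outputs separate modification from none?**

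Two scenarios were simulated, 20,000 trials each, with 52 control and 55 treatment participants, an evenly split two-level characteristic and an average effect of 0.50 SD.

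- Scenario A: interaction 1.08 SD, no slope on the characteristic in controls.
- Scenario B: no interaction, slope 0.555 SD in both arms.

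The slope in B was chosen to make the point. With an even split, the additive model averages the two arm slopes by arm size, so A gives (52 × 0 + 55 × 1.08)/107 = 0.555.

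| Mean estimate (SD) | A | B |
|---|---|---|
| Unadjusted difference | 0.50 | 0.50 |
| Adjusted difference | 0.50 | 0.50 |
| Adjusted minus unadjusted | 0.000 | 0.000 |
| Coefficient of the characteristic | 0.55 | 0.55 |
| Interaction term (not in the plan) | 1.08 | 0.00 |

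A separate simulation with 200,000 observations agrees. The additive model gave a treatment coefficient of 0.49 both when the effect was constant at 0.5 and when it was 0 in one subgroup and 1 in the other. The interaction estimates were 0.01 and 1.01.

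**3. How precisely could the interaction be estimated?**

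The documents give no alpha, power, SD or demographic composition, so there is no figure of the plan's own to reproduce. Inputs: arm sizes 52 and 55 (section IV, Data collection). Assumed: all 107 analysed, SD 1, two-sided alpha 0.05, 80% power.

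- SE of the group effect = √(1/52 + 1/55) = 0.193. The multiplier is 1.96 + 0.84 = 2.80.
- Age, per SD: SE 0.193; detectable 0.54; 95% half-width 0.38.
- Two-level characteristic with prevalence p: SE = 0.193/√(p(1 − p)).
  - p = 0.5: SE 0.387; detectable 1.08; half-width 0.76.
  - p = 0.2: SE 0.484; detectable 1.35; half-width 0.95.
- One pairwise contrast among three equal levels: SE = 0.193 × √6 = 0.474; detectable 1.33; half-width 0.93.
- Power for a 0.5 SD two-level interaction: 25% (p = 0.5) and 18% (p = 0.2).
- With t on 94 degrees of freedom (107 − 13: intercept, group, one term for each of ten covariates, one interaction), the age and two-level figures become 0.55, 1.10 and 1.37.

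**4. Multiplicity**

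Three characteristics by three outcomes is nine models. Nine independent 5% tests would give 1 − 0.95⁹ = 0.37, a 37% chance of at least one false positive.

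**The case against.** **The wording is ambiguous.** The sub-question never uses the language of moderation. Read together with the statement that stratification is done through covariates, it could mean whether demographics account for the group difference, and comparing the t-test with the regression goes some way to answering that. This is fair, and it is why the point rests on the most natural reading. No looser reading makes the listed analyses informative about effect modification, and if a looser one was meant the document should say so.

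**The hypotheses document may cover it.** It sits in a methods and analysis folder and could specify the moderation analysis. This stands as a limit: nothing here shows that the study as a whole lacks the analysis. But the present document has its own Methods list, and that list omits it.

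**The analysis would be weak.** Power of 18% to 25% for a 0.5 SD interaction, in a feasibility study whose recruitment is over, will rarely settle anything. That is a reason to report estimates with intervals instead of tests. It does not justify leaving a question asked five times without a method.

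**The figures are illustrative.** They are. Across the sample sizes the document mentions, with near-equal arms, the detectable interaction at 50% prevalence runs from 1.20 SD (N = 87) to 1.01 SD (N = 123). If the covariates explained 25% of the variance (an assumption), 1.08 would fall to 1.08 × √0.75 = 0.94. More levels for race would use more degrees of freedom. Outcomes from the same people are unlikely to be independent, so 37% is only a guide. The slope in scenario B was tuned, as stated above. The conclusion depends on none of these numbers.

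**Conclusion.** The concern holds for this document. On its most natural reading, a stated research question has no matching analysis: everything listed is a t-test or covariate adjustment. The absence of an interaction or subgroup analysis follows directly from the text; that the sub-question asks for one is a judgement about its wording. The primary comparison and the feasibility rule are not affected.

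Under the assumptions above, the trial could detect interactions of about 0.54 SD per SD of age, about 1.1 to 1.4 SD for a two-level characteristic at 50% to 20% prevalence, and about 1.3 SD for one contrast among three equal levels. The added analysis would therefore be exploratory estimation with wide intervals. It is still a cheap improvement on having no answer.

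**What to change.** State in section II what the sub-question means. If it concerns variation in the treatment-control difference, add the following to section VI:

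- For each of knowledge, skills and self-efficacy, after the primary regression, fit three exploratory models that add in turn group × age (continuous), group × race and group × ethnicity.
- Fix the coding of race and ethnicity beforehand, and say whether any other demographic is included, since the question names age and race/ethnicity only as examples.
- Report interaction estimates with 95% confidence intervals, labelled exploratory and kept outside the feasibility rule.
- State that main-effect demographic coefficients and the adjusted-versus-unadjusted comparison will not be used to answer this question.
- Section V (Recruitment) says: "The recruitment period for IN-HOME lasted from May 15, 2023 to August 16, 2023". If the models are added after data collection, date them as later specified.

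If a looser meaning was intended, reword the question to match the analysis that answers it.

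The cost is nine extra models on variables already listed as covariates, with no new data. The downsides are the wide intervals and the multiplicity shown above, which is why the results should stay exploratory.

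### Each outcome has two unranked between-arm posttest tests, and the regression omits the pretest score: the all-three feasibility verdict stays at or below 5%, but single-outcome claims have no error control

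*Combined protocol and SAP*

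**What the plan says.** Section I sets the decision rule: "IN-HOME is feasible if the treatment group shows statistically significant higher mean scores in knowledge, skills, and perceived self-efficacy at posttest compared to the control" arm. The next two sentences name the analysis ("We will use covariate-adjusted ANCOVA to control for group differences") and the sidedness ("We will use two-tailed tests to identify potential iatrogenic effects"). No significance level appears anywhere.

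The Methods at the end of Section VI list two between-arm analyses of the same posttest scores. The first is a t-test of each outcome's "composite score at pretest and posttest". The second is a regression with the "posttest composite score as the dependent variable and group assignment as the primary independent variable", adjusted for ten baseline characteristics. The pretest composite is not among those ten, although Section VI creates it for every outcome. The Methods neither rank the two analyses nor use the term ANCOVA.

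Section II also asks about outcomes one at a time. Question 3 concerns knowledge gains. Question 4 asks how far IN-HOME-trained workers "are more prepared to provide support to male caregivers compared to the control group". No multiplicity method or hierarchy is given. Section II refers to a separate hypotheses document that is not part of the public file.

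**The concern.** Two tests of one contrast can disagree. An unadjusted t-test and a covariate regression on the same 107 people will sometimes fall on opposite sides of the threshold. If the plan does not say which one counts, the favourable one can be cited, and the error rate for that outcome then rises above the level of either test.

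Three outcomes add a second layer. If they are reported one by one, as the Section II questions invite, the chance that at least one is falsely significant is well above the level of a single test.

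The plan also leaves unused what is likely to be the best predictor of the posttest score. Whenever the pretest composite predicts the posttest composite, adjusting for it makes the treatment contrast more precise. The reader cannot tell whether the ANCOVA of Section I was meant to include it.

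**Working it through.** The plan states no alpha, power, effect size or SD, so it has no figure to reproduce.

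**Inputs from the document**
- Arms: 52 control and 55 treatment (Data collection), 107 in all.
- Tests: two-tailed (Section I).
- Rule: all three outcomes significantly higher under treatment (Section I).

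**Assumed inputs**
- Alpha 0.05 two-sided, so 0.025 in the favourable direction.
- 12 covariate terms for the ten listed characteristics, since several are categorical.
- Covariates explain 10% to 50% of outcome variance.
- Correlation between outcomes 0.1 to 0.8.
- 8,000 simulated trials per null setting and 20,000 per setting in step 1.

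**Step 1. The all-three verdict.** A false verdict needs at least one truly null outcome to come out significantly favourable. Its probability cannot exceed that outcome's own error.
- One test: at most 0.025.
- Either test allowed: at most 0.025 + 0.025 = 0.05.

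The worst case has two outcomes truly and strongly improved and one null. Simulated at outcome correlation 0.5:

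| Variance explained by covariates | Adjusted test only | Either test |
|---|---|---|
| 10% | 2.7% | 3.8% |
| 30% | 2.6% | 3.9% |
| 50% | 2.5% | 4.4% |

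Across repeat runs the either-test figure lay between 3.7% and 4.6%. With all three outcomes null, the verdict was false in under 1% of trials with one test and about 1% at most with either.

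**Step 2. One outcome, either test counted, no true effect.**

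| Variance explained by covariates | Two-sided | Favourable direction |
|---|---|---|
| 10% | 7.1% to 7.3% | 3.5% to 3.7% |
| 30% | 7.4% to 8.4% | 3.6% to 4.4% |
| 50% | 8.3% to 8.9% | 4.2% to 4.7% |

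Either test alone stays near 5% two-sided. The inflation grows with the variance explained, because the two tests then agree less often.

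**Step 3. Any of three outcomes, no true effect.**
- One test each, independent outcomes: 1 − 0.95³ = 14.3% two-sided; 1 − 0.975³ = 7.3% favourable.
- One test each, simulated: 10.1% to 15.0% two-sided; 5.1% to 7.8% favourable. The top value differs from 14.3% by 0.7 points. The simulation standard error is √(0.143 × 0.857 / 8,000) = 0.4 points, so the difference is within noise.
- Either test, simulated: 13.8% to 22.1% two-sided; 6.9% to 11.8% favourable.
- Treating the six tests as independent gives 1 − 0.95⁶ = 26.5%. This overstates the problem, because the two tests of one outcome are strongly correlated.

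**Step 4. After the change.** One test with all three required gives a worst case of 2.5% favourable. Holm on the three deciding tests starts at 0.05/3 = 0.0167 and holds any-of-three claims at 5% or less.

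**The case against.** A reader might infer that the feasibility verdict itself carries a false-positive rate above 5%. The document does not support this. The rule in Section I asks for "statistically significant higher mean scores in knowledge, skills, and perceived self-efficacy at posttest", and read as written that means all three together. Such a rule needs no alpha split, and step 1 keeps it within 5% even if the better of two tests is taken for every outcome. It would exceed 5% only if one significant outcome were treated as enough.

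A reader might also infer that no deciding test is named anywhere. That is too strong. Section I names ANCOVA directly after the rule, and in Section VI the word primary is attached to the regression and not to the t-tests. What remains is that Section VI does not carry this through: it lists the t-test beside the regression without a label, and its covariate list does not settle whether the ANCOVA includes the pretest.

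The Section II questions are phrased as matters of extent and carry no significance criterion. The unseen hypotheses document may contain a hierarchy. For a Phase 1 feasibility evaluation, calling these questions exploratory would be a legitimate answer, so Holm is one option and not a necessity. It is also fair that a claim of benefit is one-directional. In that direction the per-outcome rate with either test is below 5%, though above its nominal 2.5%.

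Finally, Holm on three posttest contrasts might seem not to answer a question about gains. For knowledge it does: once the pretest composite is a covariate, regressing the gain or the posttest score gives the same treatment coefficient. Preparedness is a different matter, because it is not one of the three outcomes in the rule.

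**Conclusion.** The point holds as a gap in specification with a measurable effect on single-outcome claims. The operative Methods leave two between-arm tests unranked, omit the pretest composite from the listed covariates, and give no error control for outcomes claimed singly.

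The feasibility verdict is not inflated beyond 5%, though letting either test count raises its worst case from about 2.5% to about 4% to 4.6%. The excess belongs to single-outcome claims: about 7% to 9% two-sided for one outcome if either test counts, and for any of three about 10% to 15% with one test or 14% to 22% with either. Favourable-direction rates are about half of these.

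All of these figures rest on the assumed 0.05 level. The simulated ones also rest on the assumed covariate strength and outcome correlations. The public file cannot show whether the separate hypotheses document resolves any of this.

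**What to change.** In Sections I and VI:

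- Name one deciding test per outcome: the treatment coefficient from an ANCOVA of the posttest composite on group, the listed baseline characteristics and that outcome's pretest composite, at two-sided 0.05.
- State that feasibility requires all three coefficients to favour treatment at that level.
- Label the posttest t-tests descriptive, supporting no conclusion.
- For single-outcome claims, either apply Holm across the three deciding tests or label the claims exploratory.
- State which composite represents skills, since the variable names in Section VI cover knowledge, self-efficacy and two others (att and int) but none is evidently for skills. Treat preparedness as exploratory unless it is tied to one of the three outcomes.

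The cost is wording, one extra model term per outcome, and slightly less power for single-outcome claims if Holm is chosen. The all-three verdict is unaffected by Holm. Data collection and sample size do not change. The document already reports recruitment as finished on August 16, 2023. If outcome data had been seen before the choice is made, it should be disclosed as made after data collection.

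### The only listed tests of pretest-to-posttest change are separate within-arm t-tests, which cannot answer research question 3 on whether IN-HOME produces greater gains than control

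*Combined protocol and SAP*

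**What the plan says.** Research question 3 (section II) is comparative: "To what extent do CHWs exposed to IN-HOME show greater gains in knowledge compared to the control group".

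The Methods list at the end of section VI, Data analysis, has three entries:

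- "Between groups t-tests on each outcome’s composite score at pretest and posttest". These compare levels at each time point, not change.
- "Within group t-tests between each outcome’s pretest and posttest composite scores". These test change, one arm at a time.
- A regression with each outcome's "posttest composite score as the dependent variable and group assignment as the primary independent variable, while controlling for participant characteristics at baseline". The named covariates are participant characteristics; the pretest composite is not among them.

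Step 4 of the same section creates gain scores: "Subtract the t1 composite variables from the t2 composite variables to get the change in composite score from pretest to posttest for each outcome area". No entry in the Methods list compares these scores between arms.

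The decision rule is in section I: "IN-HOME is feasible if the treatment group shows statistically significant higher mean scores in knowledge, skills, and perceived self-efficacy at posttest", judged against the control group and paired with covariate-adjusted ANCOVA.

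**The concern.** A within-arm test asks whether that arm's mean score moved. In this design either arm may move for reasons unrelated to IN-HOME. The control arm is active and is retested: "Control participants will complete a pretest before and a posttest after reviewing caregiver information". The same applies to the treatment arm with its own material. Each within-arm p-value therefore combines retest effects, learning from whatever was read and, in the treatment arm, any effect specific to IN-HOME.

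Setting a significant result in one arm beside a non-significant result in the other does not repair this, because the difference between the two arms is never estimated. An analyst who turns to the Methods for something to say about gains finds only this pair of p-values. At stake is a report that IN-HOME participants gained and controls did not when the true gains are the same, or a significant gain that is only a retest effect.

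**Working it through.** The plan states no effect size, SD, power or alpha, so there is no figure of its own to reproduce. The check asks how often the misleading pattern appears when the true gains are equal.

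**Inputs**
- Arm sizes: 55 treatment and 52 control, the bracketed counts under Data collection. That they are the analysed numbers is an assumption.
- Sidedness: two-sided, from section I ("We will use two-tailed tests to identify potential iatrogenic effects").
- Alpha: 0.05, assumed.
- Test: a paired t-test in each arm. Pairing is inferred from the merge of pretest and posttest by participant ID under Data cleaning.
- True gain d: mean change divided by the SD of change, the same in both arms. The plan gives no value, so a range is shown.

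**Formula.** The arms are independent, so

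P(treatment only) = p_T × (1 − p_C)

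Here p_T is the chance of a significant improvement in the treatment arm and p_C is the chance of any significant change in the control arm. Both come from the noncentral t distribution with n − 1 degrees of freedom and noncentrality d√n. If both arms have the same power p, this is p(1 − p), with a maximum of 0.25 at p = 0.5.

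**Results, 55 and 52 per arm**

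| d | p_T | p_C | P(treatment only) |
|---|---|---|---|
| 0 | 0.025 | 0.050 | 0.024 |
| 0.1 | 0.109 | 0.109 | 0.097 |
| 0.2 | 0.307 | 0.293 | 0.217 |
| 0.276 (peak) | 0.520 | 0.497 | 0.262 |
| 0.3 | 0.589 | 0.565 | 0.257 |
| 0.4 | 0.830 | 0.808 | 0.159 |
| 0.5 | 0.954 | 0.943 | 0.055 |
| 0.6 | 0.992 | 0.989 | 0.011 |

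For example, at the peak 0.520 × (1 − 0.497) = 0.262. Table entries use unrounded powers. At d = 0, counting a significant change in either direction in the treatment arm gives 0.05 × 0.95 = 0.048 instead of 0.024.

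A simulation of 100,000 trials gave 0.220, 0.260 and 0.160 at d = 0.2, 0.27 and 0.4.

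**Other sample sizes in the plan.** With 60 per arm (section I) the maximum is 0.250, near d = 0.26. With 44 and 43 (the 87 CHWs of section I, split evenly) it is 0.255, near d = 0.31. The result does not depend on which count applies.

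**The comparison that answers the question.** In the same simulations, a between-arm t-test on the gain scores was significant in 5.0% to 5.1% of trials, and in favour of IN-HOME in about 2.5%, at all three values of d.

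**The case against.** The strongest reply is that the plan never misuses these tests. Nothing in it says that within-arm p-values will be set against each other, read as a treatment effect or used for a decision. The feasibility rule is a between-arm comparison at posttest, supported by the posttest t-tests and the regression. A significant change within an arm, reported as just that, is a true statement about that arm. This stands, and it limits the point to statements about gains.

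A reader might infer that the trial has no valid route to research question 3. The documents do not support that. Under randomisation the arms have the same expected pretest score, so, setting aside differential loss, the expected posttest difference equals the expected difference in gain. The posttest t-test and the regression already target that quantity, though neither uses the pretest score. What is missing is a stated link from question 3 to a between-arm estimate. Section II refers to a separate hypotheses document that is not reproduced; it may supply the link, which cannot be checked here.

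A reader might also take one in four as the expected error rate. It is a peak, reached when within-arm power is near 50%; with a large common gain both arms are significant and the pattern all but disappears. Nor should the peak be compounded over the three outcomes: 1 − (1 − 0.25)³ = 0.578 requires independent outcomes, yet all three are measured on the same people, and the feasibility rule names all three together rather than any one.

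What remains is that the within-group tests stand beside the between-arm analyses with no descriptive label and no rule for reading them.

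**Conclusion.** The point holds for claims about gains. The listed tests of change cannot show that IN-HOME produces greater gains than control. If their results are compared across arms, equal true gains give a treatment-only pattern in about 2% to 26% of trials for common gains from 0 to 0.4 SD of change. The rate falls to 5.5% at 0.5 and 1% at 0.6. A direct between-arm test favours IN-HOME wrongly in about 2.5%. These figures assume alpha 0.05, 55 and 52 analysed, and equal standardised gains; since the plan gives no expected gain or SD, the whole range applies.

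The feasibility conclusion is not undermined, and the documents do not show that the sponsor intends the invalid comparison. This is a cheap improvement that closes off a misleading reading.

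**What to change.** 1. Replace the within-group t-tests with each arm's mean pretest-to-posttest change and its 95% CI, labelled descriptive, without p-values.
2. State that no effect claim rests on a within-arm result or on comparing within-arm results between arms.
3. Name the analysis that answers research question 3: a between-arm estimate with its CI. The preferred choice is the planned posttest regression with the pretest composite added as a covariate. The alternative is the between-arm difference in the gain scores from step 4. The preference is for precision. With equal SDs at both times and pretest-posttest correlation r, outcome variance relative to the raw posttest is 1 − r² after pretest adjustment and 2(1 − r) for the gain score. At r = 0.5 these are 0.75 and 1.00; at r = 0.7 they are 0.51 and 0.60. The values of r are illustrative.
4. The text describes recruitment as complete. If outcome data have already been examined, date the change and say so.

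The cost is a few sentences and the loss of the within-arm p-values. No new data are needed, since the pretest composites and gain scores are already part of the plan.
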